This study aims to determine the effectiveness of a mindfulness-based intervention (MBI) on the reduction of posttraumatic stress disorder (PTSD) symptoms (primary outcome) and depression substance use disorder (SUD), inflammation, and cortisol reactivity (secondary outcomes) in homeless women with PTSD. Biological markers (i.e., cortisol reactivity, C-reactive protein [CRP]) of the stress response will be evaluated as correlates of MBI treatment-response will help clarify mixed findings regarding dysregulation of the HPA-axis as a function of amount, type, and timing of trauma exposure. It will advance theory regarding the use of MBIs for PTSD while exploring biological markers that might maintain PTSD symptoms over time. The project has the potential to bolster the capacity of service providers to offer feasible and acceptable MBI interventions to homeless women and other vulnerable populations. If the proposed aims are achieved, they may provide several valuable insights. They will examine the efficacy of MBI to address PTSD in homeless women (inform & improve services, interventions, treatments); improve on methodological limitations of prior research on MBIs for PTSD (including small sample sizes, lack of attention control group, incomplete trauma history); and explore biological markers that correlate with PTSD-symptom maintenance or reduction post-MBI (expand concepts). Importantly, the MBI that will be used in the intervention was the product of a rigorous preliminary mixed-methods inquiry that including a Community Advisory Board (consisting of site staff, clinicians, and homeless women) and focus groups with women from the community (i.e., homeless women currently residing at a residential drug treatment facility). The results of these formative activities resulted in the modification of an evidenced-based MBI - Mindfulness-based Stress Reduction (MBSR) for cultural sensitive and appropriateness, increasing acceptability and feasibility. Importantly, findings from this proposal may provide a low-cost method to improve services for homeless women as they begin to answer key theoretical questions regarding the relationship between biological markers of stress regulation and reactivity, the inflammatory response, PTSD and related comorbidities (SUD, depression), and MBIs.

Subsection 1A.2 - Overall Structure of Study Team

Subsection 1A.3 - Research Team and Responsibilities

Principal Investigator (PI): [name] [name].

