Space/time needed			1 meeting per week (1-2 hours)		Four meetings total, each 2 hours		1 weekly meeting (1-2 hours) for 4 weeks		Screening space 1-2 days/week per site	Room for intervention 1 X per week at each site for 1-2 hours (same time each week)		
YEAR 2 (2021))											
	21-Jan	21-Feb	21-Mar	21-Apr	21-May	21-June	21-July	21-Aug	21-Sept	21-Oct	21-Nov	21-Ded
PRIMARY ACTIVITIES	Recruit Cohort 2	MBI & HP C2	2		Recruit Cohort 3	MBI & HP C	ohort 3		Recruit Cohort 4	MBI & BP Co	hort 4	
Space/time needed	Screening space 1-2 days/week per site	Room for inte X per week a for 1-2 hours time each we	ervention 1 It each site (same eek)		Screening space 1-2 days/week per site	Room for in X per week for 1-2 hour each week)	Room for intervention 1ScX per week at each sitespfor 1-2 hours (same timedaeach week)pe		Screening space 1-2 days/week per site	Room for intervention 1 X per week at each site for 1-2 hours (same time each week)		
Follow-up	·			Cohort 1 follow- up	·			Cohort 2 follow-up	·		ł	Cohort 3 follow-up
YEAR 3 (2022))											
	22-Jan	22-Feb	22-Mar	22-Apr	22-May	22-June	22-July	22-Aug	22-Sept	22-Oct	22-Nov	22-Dec 23 Jan- Feb
PRIMARY ACTIVITIES	Recruit Cohort 5	MBI & HP Co	phort 5			Recruit Cohort 6-7	MBI	Cohorts 6-7				
Space/time needed	Screening space 1-2 days/week per site	Room for inte X per week a for 1-2 hours time each we	ervention 1 It each site (same eek)			Screening space 1-2 days/week per site	Room for intervention 1 X per week at each site for 1-2 hours (same time each week)					
Follow-up				Cohort 4 follow up		·	Cohort 5 follow up				Cohorts 6 ups	6-7 follow

6 - Basic Definitions

Mindfulness: The process of focusing one's attention on the present moment (including thoughts, feelings, and sensations) without judgement (Kabat-Zinn, 1990; Lang, 2017).

Mindfulness-Based Stress Reduction (MBSR): MBSR is an 8-week, 9 session manualized mindfulness-based intervention that is appropriate for participants from different religious, spiritual, or ethnic background and is not grounded in religious ideology. During MBSR, participants will be trained in mindfulness meditation and the applicability of mindfulness to daily life.

Post-traumatic Stress Disorder (PTSD): PTSD is a psychological pathology characterized by re-experiencing, avoidance, negative thoughts or cognitions, hyperarousal after experiencing a traumatic event.

Trauma: According to the DSM-5, must involve actual or threatened death, serious injury, or sexual violence.

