In Phase II, we will assess the potential benefit of MBSR to reduce PTSD (primary outcomes) and secondary outcomes (e.g., depression, SUD, CRP, cortisol reactivity), among 130 eligible homeless women who exhibit likely subthreshold or threshold PTSD living at one of two residential drug treatment facilities. MBSR will be compared to an attention-control group (Health Promotion Wellness Classes; HP). There originally intended to be five cohorts of women, each with 12-15 women (total of 24-30 women per cohort). However, due to COVID-19 adjustments have been made in terms of the class size and randomization procedure. At each cohort, sites will be randomized to receive either the MBSR or the HP. Although sites will alternate between MBSR and HP by cohort, each participant will receive either the MBSR or the HP. Randomization will occur using RedCAP. The women participate in either MBSR or HP for 9 weeks. Psychosocial data will be collected at baseline, immediately following final intervention session, and at 6-month follow-up via tablet questionnaires. After psychosocial data collection, a stress task (Trauma Imagery Task) will be conducted at each time point, with saliva collected both before and after the task to assay cortisol and CRP. This proposal will improve on the methodological rigor of prior research on MBIs for PTSD in disadvantaged populations by using: randomization procedures that account for cross-contamination; blind evaluators; longitudinal follow-up; an attention control group equal to the MBI intervention in both contact visits and hours; increased demographic diversity; comprehensive lifetime trauma assessment; and inclusion of objective indices of stress responses to accurately evaluate the effectiveness of MBIs in treating trauma-related symptoms.

Confidentiality and Ethical Issues

All program staff must follow confidentiality and ethical procedures throughout this program to ensure that everybody is treated with respect and dignity.

1. Communication with study participants must remain confidential. To maintain confidentiality for participants, any personal information provided, such as participants' name, age, etc., will

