The following will **not** be eligible for participating:

- 1) Persons who are:
 - a. Not able to speak English
 - Judged to be cognitively impaired, as indicated by score > 10 on the Short-Blessed Screener

Subsection 2.6 - Phase II Laboratory Tests/Sample Collection

Saliva Sampling and Results

Saliva Collection

- Pre-task, saliva will be collected. All saliva collection will occur between 10am-2pm to minimize diurnal fluctuation effects. (Study procedures may start before 10, but first saliva sample must be collected after 10:00am; the second sample must be collected before 2pm participants must be scheduled according to these specifications).
- Two whole saliva samples will be collected using an unstimulated passive drool technique.
- Women will be instructed to avoid eating, brushing teeth, or smoking for one hour prior to the assessment and will be asked to wait to begin the task if they have.
- Participants will rinse their mouths thoroughly with water for 10 minutes before samples are collected. Participants will then passively drool into a collection vial for three minutes or until 0.80 milliliters of fluid is collected.
- Saliva samples will be immediately placed in the on-site freezer (or ice cooler) and be taken to IISBR within 36 hours to be frozen at -80°C until assayed.
- All samples will be assayed for salivary cortisol and CRP using a highly sensitive enzyme immunoassay (Salimetrics, IISBR).
- **Twenty minutes after task completion**, saliva samples will be collected again in an identical manner to that described above.
- Participants will then be offered snacks and a drink and be debriefed to ensure they are not experiencing severe task-related psychological distress. In the unlikely event of participant distress, an immediate referral will be made to on-site professional staff.

Subsection 2.7 - Phase II Intervention Program Description

General Description: Among 134 eligible trauma-exposed homeless women, assess the impact of the MBSR intervention program PTSD symptoms (primary outcomes), and substance abuse, depression, cortisol reactivity, and inflammation (secondary outcomes).

Data Collection Time points: Baseline, 2 months, and 6 months

Total Duration: 6 months

The following sections will outline the intervention process:

- Pre-intervention Assessments
- Brief Stress Task (Trauma Imagery Stress Task)
- Biospecimen Collection
- Biospecimen Analysis
- MBSR Intervention
- Health Promotion Intervention
- Post-Assessment

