- Team Management of Biospecimen Collection Refusal
- Dealing with Program Attrition

Subsection 2.8 - Phase II Pre-intervention Assessments

After Informed Consent, participants will complete a series of self-report measures. These measures will be administered by Research Staff at a private location at the site. Responses options to each question will be provided to the participant, organized in a clearly labeled binder. The Research Staff will display the response options for each measure, read the options out loud, and then record the response on the tablet. At the end of each measure, the RA will "lock" the measure. There will be a prompt if any items have been missed. Please check that there is no missing data. The participant may take a break at any time. However, the participant should refrain from eating, drinking (except for water ~ 10 minutes prior to stress task), or smoking until after the second saliva collection to ensure the accuracy of the saliva sample.

Order of assessments

- 1. Drug test (urine)
- 2. TCU Drug Screen (self-report)
- 3. Self-compassion scale short form
- 4. General self-efficacy scale
- 5. Mindful Attention Awareness Scale
- 6. Difficulties I Emotion Regulation Scale
- 7. Satisfaction with Life Scale
- 8. Quality of Life Enjoyment and Satisfaction Questionnaire
- 9. MOS Social Support
- 10. Perceived Stress Scale
- 11. Dimensions of Anger Reactions
- 12. PROMIS Anxiety
- 13. PROMIS Depression

*NOTE: For time constraints, the urine test can be administered during the waiting period prior to the second cortisol sample.

AT THIS POINT, THE FIRST SALIVARY SAMPLE IS COLLECTED

14. Negative Life Events Inventory

15. PCL 5- *Worst life event* (this is the event that bothers them the most, from their entire life)
16. PCL 5 - *Recent (past year)* this is a traumatic event that has happened to them recently (in the past year) - it may or may not be the same as #16

17. Trauma Imagery Stress Task (the Negative Life Events Inventory and the PCL build up to this)

Subsection 2.9 - Phase II Brief Stress Task (Trauma Imagery Task)

After completing the PROMIS Depression, the participant will provide a saliva sample. They will then complete the negative life events inventory and the PCL 5 (for worst event in their life and a recent event). The reason that the saliva sample is taken before these measures and not directly before the Trauma Imagery Task is because in pilot studies the women began to

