become distressed when recounting their traumas during the Negative Life Events Inventory and the PCL; thus, the "baseline" for cortisol is now taken PRIOR to these items.

After completing the PCL for worst event and recent event, the participant will complete a a modified script-driven imagery task (Seo et al., 2013), derived from prior research with women with PTSD. Participants will be asked to recount a traumatic event via written response. The RA will provide a paper and pen and instruct the participant to recall the event exactly as it happened. The RA can offer prompts to recall sight, smell, and sound. The participant will then recount the event to the RA. Script driven imagery tasks have been effectively and safely used to assess traumatic-stress responses in individuals with PTSD. However, RAs will be highly trained to assess any severe distress that may arise and will immediately notify the PI and site clinical staff immediately. Responses will be subsequently destroyed. *AFTER THE COMPLETION OF THE TRAUMA IMAGERY TASK THE 20 MINUTE POST-SALIVA SAMPLE TIMER STARTS!* When the timer starts, the RA will not interact with the participant. They should sit quietly or may read.

Subsection 2.10 - Phase II Biospecimen Collection

Urine Collection: Participants will provide a urine sample to validate self-report drug use. A 5panel FDA-approved urine test cup will be used in this study. The participant will be instructed to urinate in the cup, close the cup, and then bring it back to the RA to read. Gloves will be used at all times and the RA should read the cup without touching it if possible. The participant will then be instructed to dispose of their urine in the restroom.

Saliva Collection: Before and twenty minutes after the brief stress task (Trauma Imagery Stress Task), women will be asked to provide a salivary sample. Women will be instructed to avoid eating, brushing teeth or smoking for one hour prior to the collection of saliva and will be asked to wait to begin the task if they have. Participants will passively drool into a collection vial for three minutes or until 0.80 milliliters of fluid is collected.

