Mindful awareness attention scale (MAAS): is a 15-item scale designed to assess a core characteristic of mindfulness, namely, a receptive state of mind in which attention, informed by a sensitive awareness of what is occurring in the present, simply observes what is taking place (Brown & Ryan, 2003; Carlson & Brown, 2005).

Five facet Mindfulness Questionnaire (FFMQ) is a 39 item questionnaire that assesses five independent sub-scales: observing, describing, acting with awareness, non-judging of inner experience, and non-reactivity to inner experience (Baer et al., 2008).

Life event history: Life events history will be assessed by asking respondents whether they ever experienced each of 40 specific negative life events (NLEs; will include both trauma and stressors), and, if so, at what age(s) this occurred. This will also be updated with respect to recent events upon immediate completion of the 9 week courses as well as at the 6-month follow up. The measure was modified from the Diagnostic Interview Schedule trauma section (Robins, Helzer,

Croughan, & Ratcliff, 1981) by including several stressful or traumatic events reported by primary care patients ([name], Silver, & Waitzkin, 2000) and has provided rates of events comparable to other community-based studies (e.g., Seery et al., 2010).

Emotion regulation: will be assessed with the Difficulties in Emotion-Regulation Scale (DERS; Gratz & Roemer, 2004; Kaufman et al., 2016), short form. DERS is a 18- item questionnaire that aims to measure how much one is able to regulate/deregulate their emotions. The 41 questions are based off of six factors including acceptance of emotions, impulsiveness, ability to work towards goals, awareness of own emotions, clarity of emotions, and accessibility to emotion-regulation strategies

Social support will be assessed using the MOS Social Support scale (Sherbourne & Stewart, 1993) This 19 item measure assesses social support.

Anxiety: will be assessed using the PROMIS measure for anxiety (Emotional Distress). The 8-tem form will be used. It assesses symptoms of Generalized Anxiety Disorder. it is desirable to use the 8-item short form, which has reliability and validity comparable to the 28-item computer adaptive form (PROMIS Health Organization, 2019).

General Self-efficacy scale: This 10-item scale was created to assess a general sense of perceived self-efficacy (Schwarzer & Jerusalem, 1995).

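### Saliva clock time can vary within a four-hour window and the gap between samples is not fixed, yet the SAP does not require any cortisol model to adjust for time of day

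*Combined protocol and SAP*

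**What the plan says.** Protocol Section 2.6 sets the window: "All saliva collection will occur between 10am-2pm to minimize diurnal fluctuation effects". It adds the bounds: "first saliva sample must be collected after 10:00am; the second sample must be collected before 2pm participants must be scheduled according to these specifications".

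Section 2.8 fixes where the first sample falls in the interview. After the depression scale comes the instruction "AT THIS POINT, THE FIRST SALIVARY SAMPLE IS COLLECTED". The Negative Life Events Inventory, a PCL-5 for the worst event, a PCL-5 for a recent event and the imagery task follow. Section 2.9 starts the 20-minute timer for the second sample only when the task is over. It explains that the baseline "for cortisol is now taken PRIOR to these items" because women in pilot work became distressed during them. Section 2.8 also lets the participant take breaks whenever she wishes. By contrast, the key to Table 4 (Section 2.3) and the script in Appendix II put the first sample directly before the task.

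The SAP fits random-intercept models with group, visit (T1, T2, T3), group-by-visit and site as fixed effects. Its time term means visit, not hour of day. Further covariates enter if they pass a bivariate screen and make theoretical sense, and no candidates are listed. Neither clock time nor minutes between samples is named, and the reactivity measure is not defined.

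**The concern.** Cortisol reactivity is a named secondary outcome. The protocol treats diurnal drift as real enough to need a window, but a window limits the drift without removing it. What remains goes to two places:

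- **Levels.** Two women, or one woman at two visits, may be sampled hours apart. The difference appears as noise or as change over visits.
- **Reactivity.** The second sample is always later than the first by an uncontrolled interval, so ordinary decline is subtracted from any stress response.

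A significance screen is a weak safeguard against a nuisance factor known in advance. Clock time could fail the screen in a sample of this size and still matter. At stake are precision for every cortisol result and, if timing happens to follow class, site or arm, the validity of the arm comparison.

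**Working it through.** The documents state no diurnal slope, cortisol SD, sample gap or cortisol power figure, so there is no plan figure to reproduce. What follows uses stated assumptions.

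**Inputs from the documents:** a 10:00-14:00 window (Section 2.6); about 120 women at T2 (Section 2.16); five cohorts at two sites (Sections 2.2 and 2.4); the SAP fixed effects.

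**Assumed:** a fall of s = 5% to 15% per hour; a gap between samples of 30 to 120 minutes.

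**1. Spread of comparable samples.** Sample 1 must follow 10:00 and sample 2 must precede 14:00, so sample 1 ranges over 4 h minus the gap: 4 − 0.5 = 3.5 h down to 4 − 2 = 2 h. The difference is 1 − (1 − s)^h.

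| h | s = 5% | s = 15% |
|---|---|---|
| 2 h | 1 − 0.95² = 10% | 1 − 0.85² = 28% |
| 3.5 h | 1 − 0.95^3.5 = 16% | 1 − 0.85^3.5 = 43% |

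**2. Decline inside the gap.** The same formula gives 2.5-7.8% for 30 min, 5-15% for 60 min and 10-28% for 120 min. Raw pre-to-post reactivity absorbs this. A between-arm comparison absorbs only the arm difference in gap: 15 minutes would shift it by 1.3-4.0%, and an equal gap in both arms by nothing.

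**3. Group-by-time contrast.** Bias = −slope × (difference between arms in mean clock-time change). Take log-cortisol slopes of 0.05 to 0.15 per hour (4.9-13.9% per hour, close to s) and suppose that T2 sampling at one site runs 2 h later than at the other. The arm difference in mean clock time then depends on how the five cohorts split between site and arm:

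- 3:2 (strict alternation): 2 × (3/5 − 2/5) = 0.4 h, bias −0.02 to −0.06
- 4:1: 2 × (4/5 − 1/5) = 1.2 h, bias −0.06 to −0.18
- 5:0 (site identical with arm): 2 h, bias −0.10 to −0.30

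A simulation of the T1-T2 contrast used 120 women in 10 classes of 12, an assumed residual SD of 0.5 log units and 2,000 runs per setting:

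| Timing pattern | Bias (log units) | Type I error |
|---|---|---|
| No arm pattern | about 0 | 4.3-5.2% |
| 3:2, 2 h site shift | −0.02 to −0.06 | 5.6-6.9% |
| 4:1, 2 h site shift | −0.06 to −0.18 | 7.9-27% |
| 5:0, 2 h site shift | −0.10 to −0.29 | 12-60% |
| Any shifted pattern, visit-specific clock time in the model | at most 0.005 in size | 4.5-5.8% |

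The simulated decline was linear, as was the adjustment. A site main effect is constant over visits, so it cannot remove a site-by-visit timing shift.

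**The case against.** The strongest reply is that nothing in the documents shows a timing difference between arms. If there is none, the group-by-time contrast is sound, and the simulation agrees. That stands, and it limits the point to avoidable variation plus conditional bias.

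Three stronger readings are tempting but not supported:

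- **T2 saliva is tied to the class slot.** Section 2.1 says "Psychosocial data will be collected at baseline, immediately following final intervention session, and at 6-month follow-up via tablet questionnaires", and the calendar gives "Room for intervention 1 X per week at each site for 1-2 hours (same time each week", so a reader might infer that T2 cortisol is taken straight after class at an hour set by the class. But no class clock time is given and same-day saliva is not stated. Sections 2.2 and 2.14 say only that T2 comes after the ninth session, and the 10:00-14:00 rule still binds. Questionnaires are given one to one, so 13-14 women cannot all be sampled at one hour.
- **Trauma history lengthens the gap.** The inventory covers 40 events "and, if so, at what age(s) this occurred" (Appendix IV), and Section 1A.1 speaks of dysregulation "as a function of amount, type, and timing of trauma exposure". Each endorsed event does add a question between samples, so a longer gap is plausible. No durations are given, however. At T2 and T3 only recent events are updated, and the SAP contains no trauma-cortisol model.
- **The whole window counts.** Four hours at 5-15% gives 19-48%, but that sets a first sample at 10:00 against a second sample at 14:00. Section 2.6 does not allow like-for-like samples that far apart.

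Two further objections shape the remedy. The inventory and PCL-5s are themselves distressing, so minutes between samples partly measure the stressor, and compulsory adjustment could remove real reactivity. Moving T2 to a day without class would change what an immediate assessment means and could lose women who leave the residence. Neither step is recommended here.

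Finally, the SAP's screen could admit clock time, and the REDCap forms (Appendix VII) are not reproduced, so collection times may already exist. That lowers the cost of the fix but does not supply prespecification.

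**Conclusion.** The point holds in a limited form. The plan acknowledges diurnal drift, leaves clock time free within the window and the sample interval unfixed, and requires no model to account for either. Cortisol levels and pre-to-post reactivity therefore carry variation that could be removed cheaply. On an assumed 5-15% fall per hour and gaps of 30-120 minutes, first samples can differ by about 10-43% through timing alone.

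Bias in the arm contrast is a possibility, not a finding. It is about zero without an arm pattern and small under strict alternation even with an assumed 2-hour site shift. It becomes large only if site and arm nearly coincide. Section 2.1 (sites alternate by cohort) and Section 2.2 (sites randomised before recruitment) leave the actual split unclear. The primary PTSD outcome is untouched.

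**What to change.** 1. **Protocol Sections 2.6 and 2.10:** record in REDCap the clock time of both saliva samples at every visit. Where feasible, book T2 and T3 samples near the woman's own T1 clock time.
2. **SAP:** prespecify visit-specific clock time of the first sample as a fixed covariate in every cortisol model, exempt from the bivariate screen, and define the reactivity measure.
3. **SAP:** tabulate minutes between samples by arm and visit. Adjust for them only in a sensitivity analysis, because the interval contains part of the stressor.
4. **Consistency:** reconcile the Table 4 key and the Appendix II script with Sections 2.8 and 2.9 on when the first sample is taken.

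The cost is two extra data fields, one model term and slightly tighter booking. The SAP is written in the past tense. If sampling is over, the booking step falls away, but any recoverable collection times can still enter the models, labelled as added after the fact.
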